### 3.5.5. Harms

Passive reporting of adverse effects has been used in the past for azithromycin trials. More than 800 million doses have been distributed as part of the trachoma program, and this study will be unlikely to unveil new side effects. We intend to be vigilant, and serious adverse events suspected of being drug-related will be reported to the DSMC within 24 hours of our notification.

We propose no formal statistical analysis of safety events but will report adverse events by arm.

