MORDOR I demonstrated that community-level biannual distribution of oral azithromycin to children 1–59 months of age reduced mortality by nearly 14% compared to placebo over 2 years in Malawi, Niger, and Tanzania.⁴ The greatest effect was found in Niger, where communities receiving azithromycin experienced an 18% reduction in mortality compared to those receiving placebo.⁴ Subgroup analyses suggested that the youngest children might benefit the most, with reductions of approximately 23% in children 1–11 months old.⁴ In Niger, azithromycin distributions were associated with an increase in antimicrobial resistance (AMR) to macrolides after 2 years,⁵ though azithromycin remained similarly effective in reducing mortality after 3 years in MORDOR II.⁶

The World Health Organization (WHO) released conditional guidelines for this intervention which include targeting azithromycin distributions to children 1–11 months of age in high mortality settings.⁷ The rationale for targeting this age group is that the youngest children experience the highest risk of mortality and limiting distributions to the youngest children could minimize selection for antimicrobial resistance. However, distributing azithromycin to children 1–11 months alone remains untested, since MORDOR I treated children 1–59 months of age. A crude examination of relative mortality reductions by age group suggests a stronger effect in the younger age groups, but MORDOR was unable to demonstrate a differential effect by age group statistically ($P = 0.20$ for test of interaction of treatment and age).⁴ Moreover, a herd effect could have contributed to the apparent larger effect sizes in the younger groups; treating children 12–59 months may protect children 1–11 months by reducing their exposure to infectious diseases causing mortality. Finally, beyond a possible differential effect by age group, in MORDOR I–Niger there were 5 times as many children aged 12–59 months as children 1–11 months, resulting in nearly twice as many deaths averted in the older age group.⁸ The greatest societal gains may thus come from intervening on a population with a broader risk spectrum instead of targeting only the highest risk subgroups.⁹ More evidence is needed to determine the difference and magnitude of the benefit of targeting different age groups, and of the risk of inducing AMR when distributing to different age groups.

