4.4.3. Randomization, Adaptation, and Masking

4.4.3.1. Randomization

The randomization unit for the Mortality/Resistance Trial will be the grappe, which is the smallest health care unit administratively defined in Niger, hereafter referred to as “community.”

Communities will be randomized to the following 3 arms:

- Azithro 1–11:** biannual weight- or height-based dose of oral azithromycin suspension to children 1–11 months old and oral placebo to children 12–59 months old
- Azithro 1–59:** biannual weight- or height-based dose of oral azithromycin suspension to children 1–59 months old
- Placebo:** biannual weight- or height-based dose of oral placebo to children 1–59 months old

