4.4.3.3. Masking

In the Mortality/Resistance Trial, we will use a matching placebo to mask study arm allocation. Placebo will be identical to azithromycin in appearance, smell, and packaging. Treatment assignment will be masked by assigning a series of upper- and lower-case letters to each trial, age group, and treatment arm. Those masked to study arm allocation include participants, investigators, most study personnel including census personnel administering treatment and collecting mortality outcome data and the data analysis team, and laboratory personnel processing samples for resistance outcomes. Unmasked personnel include the trial biostatistician and data analyst responsible for implementing the randomization sequence and key members of Pfizer staff. Key members of the Pfizer staff must be unmasked to implement the study drug treatment allocation, and to review SAE reporting. Masking will minimize bias introduced through knowledge of treatment assignment and will ensure that the census and outcome assessments are identical in all study communities.

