4.4.7. Adverse Events Monitoring

During the consent process, the common adverse reactions that may occur will be explained to caregivers/guardians. At the time of treatment, caregivers will be instructed to report to the study team any adverse event experienced by the treated child within 28 days of treatment. Children will be referred for follow up care on a case-by-case basis.

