## 3.2. Study Methods

### 3.2.1. Trial design

AVENIR is designed as a large simple double-masked cluster-randomized trial with response-adaptive allocation (a platform, perpetual trial). The rationale for adaptive randomization is to allow all communities to have the opportunity to be treated, and to allow the program to evolve into the optimal treatment. If new treatment arms are added to AVENIR in the future, or if any of the current treatment arms are discontinued, the Protocol and SAP will reflect those updates.

Eligible communities in Niger will be randomly selected to participate in a mortality/resistance trial, a delivery trial or a delayed intervention.

In the mortality/resistance trial, communities will be randomized to one of three azithromycin distribution strategies: 1) **azithro 1-11**: biannual oral azithromycin to children 1-11 months old with biannual oral placebo to children 12-59 months old, 2) **azithro 1-59**: biannual oral azithromycin to children 1-59 months old, or 3) **placebo**: biannual oral placebo to children 1-59 months old. Mortality will be monitored through biannual census data collection, which will be used to adaptively allocate treatment assignments after the first year. Communities will keep their group assignment for 4 distributions. Antimicrobial resistance will be monitored in a random subsample of treated and untreated children and adults in the Dosso region. See Figure 1 for a summary of the design.

Details are provided in the Protocol document, INV\_002454\_2019.

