#### ***Mortality primary outcomes***

*Mortality primary outcome 1:* mortality in 1-59 month olds, assessed at 2.5 years (based on at most 2 years of follow-up per community), comparing the 1-59 month and the placebo arms. Assuming a standard deviation of approximately 0.023, we find that 1,116 communities per arm will provide approximately 80% power to detect a 10% relative reduction, assuming a baseline mortality rate of 27 per thousand person-years among children 1-59 months old and an alpha of 0.05. The absolute effect size is a mortality rate difference of 2.7 deaths per 1000 person-years. This calculation is based on the standard Z-test formula for power (treating the mortality rate in each community as a continuous variable). The calculation does not involve a correction for multiple comparisons since the analysis uses a hierarchical testing approach for the three mortality outcomes, as described below.

*Mortality primary outcome 2:* mortality in 1-11 month olds, assessed at 2.5 years (based on at most 2 years of follow-up per community), comparing the 1-11 month arm and the placebo arm. Assuming a standard deviation of approximately 0.074, we find that 1,116 communities per arm will provide approximately 80% power to detect a 19% relative reduction, assuming a baseline

mortality rate of 45 deaths per thousand person-years among children 1-11 months old and an alpha of 0.05. The absolute effect size is a mortality rate difference of 8.8 per 1000 person-years. This calculation is based on the standard Z-test formula for power (treating the mortality rate in each community as a continuous variable). The calculation does not involve a correction for multiple comparisons since the analysis uses a hierarchical testing approach for the three mortality outcomes, as described below.

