*Mortality primary outcome 3:* mortality in 12-59 month olds, assessed at 2.5 years (based on at most 2 years of follow-up per community), comparing the 1-11 month and 1-59 treatment arms. Assuming a standard deviation of approximately 0.022, we find that 1,116 communities per arm will provide approximately 80% power to detect a 11% relative reduction, assuming a baseline mortality rate of 24 deaths per thousand person-years among children 12-59 months old and an alpha of 0.05. This corresponds to an absolute reduction of 2.7 in the death rate per 1000 person-years. This calculation is based on the standard Z-test formula for power (treating the mortality rate in each community as a continuous variable).

Sensitivity analyses for primary outcomes based on reduced enrollment caused by security or logistical concerns: if only the first half of Tahoua communities are enrolled by 2.5 years, with 791 communities per arm, we anticipate the following detectable relative detectable effect sizes (respectively): 12%, 23% and 13%, for 1-59 months, 1-11 months and 12-59 months.

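### The only adverse event table in SAP 3.5.5 is by arm, so the azithro 1-11 row dilutes a non-fatal infant excess for event types that older children also have

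*SAP*

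**What the plan says.** SAP 3.5.5 relies on passive reporting, sends serious events suspected to be drug-related to the DSMC within 24 hours, and then says: "We propose no formal statistical analysis of safety events but will report adverse events by arm". It mentions neither an age split nor a dose denominator. Protocol 6.13.8 has the DSMC closed reports displayed by intervention group, also without a stated age split.

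The arms differ in who receives drug. Azithro 1-11 is "biannual oral azithromycin to children 1-11 months old with biannual oral placebo to children 12-59 months old" (SAP 3.2.1). Azithro 1-59 is "biannual weight- or height-based dose of oral azithromycin suspension to children 1–59 months old" (Protocol 4.4.3.1). Caregivers are asked to report "any adverse event experienced by the treated child within 28 days of treatment" (Protocol 4.4.7), so placebo-dosed older children enter the same row as azithromycin-dosed infants.

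Related commitments:
- Numbers of treatments are to be reported (SAP 3.2.5 and 3.4.4), without a stated age split.
- The modified per-protocol analysis uses antibiotic coverage in the targeted age group (SAP 3.3.3), and Protocol Table 3 lists equity of coverage by age.
- For mortality, SAP 3.5.2 restricts azithro 1-11 versus placebo to children aged 1-11 months.
- Operational detail on adverse events is left to separate reporting procedures (Protocol 4.4.7.1) and a monitoring plan (appendix 7.11). Neither is among the documents reviewed.

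**The concern.** In two of the three arms, arm and product received coincide for every child. In azithro 1-11 they do not: the arm label marks active drug for infants and placebo for everyone else. A by-arm comparison with placebo therefore estimates the effect of the strategy on the whole population aged 1-59 months. It does not show whether infants given azithromycin had more non-fatal events than infants given placebo.

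That second question matters because treating only infants is one of the two strategies under test, and Protocol section 2 describes it as untested. The common side effects named in Protocol 4.4.3.6 (diarrhea, nausea, abdominal pain, vomiting) are not described as specific to infants, so they are the kind of event that a pooled row would dilute.

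A smaller point is that allocation adapts after the first year, with a floor of 10% per arm (SAP 3.2.2). Arms may differ in size, and event counts by arm are then hard to read without doses as a denominator.

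**Working it through.** The documents state no safety figure, so there is none to reproduce. The check has two parts: the age mix, and the dilution that follows from it.

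**Age mix.** In Protocol section 2, for the earlier Niger trial, "there were 5 times as many children aged 12–59 months as children 1–11 months". The SAP's planning rates (section 3.2.3) give a cross-check: a "mortality rate of 45 deaths per thousand person-years among children 1-11 months old", a "mortality rate of 24 deaths per thousand person-years among children 12-59 months old", and 27 per 1,000 person-years at 1-59 months.
- At 5:1 the pooled rate would be (45 + 5×24)/6 = 27.5, close to 27.
- Solving 45w + 24(1−w) = 27 gives w = 3/21 = 0.143, or 6 older children per infant.
- Rounding of the three rates allows w from 2/21 (9.5 per infant) to 4/21 (4.25 per infant).

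Person-time share stands in for dose share here. On any of these values most children in the azithro 1-11 row are of placebo age.

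**Dilution in the azithro 1-11 row.** Let k be older children per infant, r the background event rate in infants relative to older children, and R the true infant risk ratio. Infants' share of background events is s = r/(r + k). With no effect in placebo-dosed children, the row shows 1 + s(R − 1). The values r and R = 2 are assumptions.

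| r | s (k=5) | ratio shown | s (k=6) | ratio shown |
|---|---|---|---|---|
| 0.5 | 0.091 | 1.09 | 0.077 | 1.08 |
| 1 | 0.167 | 1.17 | 0.143 | 1.14 |
| 2 | 0.286 | 1.29 | 0.250 | 1.25 |
| 5 | 0.500 | 1.50 | 0.455 | 1.45 |
| infants only | 1 | 2.00 | 1 | 2.00 |

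Dilution concerns the ratio. With equal doses per arm, the excess count is the same pooled or split.

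**The azithro 1-59 row.** With risk ratio q in older children, this row shows 2s + q(1 − s). If q = 2 it shows 2.00 throughout. If q = 1 it repeats the table above. If q = 1.5, for r = 1, 2 and 5 it shows 1.58, 1.64 and 1.75 at k = 5, and 1.57, 1.63 and 1.73 at k = 6. It is a valid drug contrast and shows an all-age excess in full, but it blurs an excess specific to infants.

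**What this means for visibility.** Suppose 120 events in the placebo arm, 20 of them in infants (k = 5, r = 1), equal exposure and no clustering. Use z = ln(RR)/√(1/m + 1/(m·RR)), with m the placebo-arm count.
- Infants only: 0.693/√(1/20 + 1/40) = 2.53, so the chance of passing 1.96 is about 72%.
- Pooled: 0.154/√(1/120 + 1/140) = 1.24, so the chance is about 24%.

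The counts are invented and no test is planned. The comparison only shows how much clearer the split is.

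**The case against.** The strongest reply is that this is silence and not error. Reporting events by arm does not exclude an age split, the split could still be produced at reporting, and the unseen monitoring plan may already specify it. This stands in part. It limits the point to what the SAP and protocol text commit to, and if the plan has the split, all that is missing is a cross-reference.

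Other replies that stand:
- SAP 3.5.5 also commits to 24-hour DSMC notification, and serious events are submitted and reviewed on individual forms (Protocol 4.4.7.1). A reader might infer that by-arm counts are the only safety provision; they are not.
- Age-specific coverage is already anticipated, so dose denominators by age should be largely within reach. The gap is mainly in the event numerator.
- A reader might infer that every infant harm is diluted. The infant risk that the protocol names, hypertrophic pyloric stenosis, would be little diluted if it is confined to infants. Deaths are compared by age, with verbal autopsy planned for deaths in children treated at 1-2 months (Protocol 4.4.8.2).
- Every background ratio and risk ratio used in the working is assumed. Only the age mix comes from the documents.
- Reporting is passive, and the protocol says side effects have rarely been reported in mass distributions. Three arms by two ages will give sparse cells, and splitting does not cure under-reporting.

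None of this supplies the missing contrast, which is non-fatal events in azithromycin-dosed versus placebo-dosed infants.

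**Conclusion.** The point holds as a minor one. Followed as written, the by-arm table dilutes a non-fatal infant excess in the azithro 1-11 row for event types that older children also have. The direction follows from the design and an age mix of about 5 or 6 older children per infant. The size, a doubling shown as about 1.1 to 1.5, depends on assumed background ratios of 0.5 to 5 and on no effect in placebo-dosed children.

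Two stronger readings are not supported. One is that the by-arm table is wrong: it is the correct display for comparing strategies. The other is that a trial conclusion is at risk: the table is descriptive, and the mortality comparison for infants already uses the right age restriction. What is missing is the same restriction for non-fatal harms.

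**What to change.** Keep the by-arm table in SAP 3.5.5 as the strategy comparison. Add one sentence committing to descriptive adverse events and SAEs per 1,000 doses given, by arm within age at dosing (1-11 and 12-59 months):
- at 1-11 months, each azithromycin arm versus placebo;
- at 12-59 months, azithro 1-59 versus the two arms that give placebo at that age.

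No formal test is needed. If the adverse event monitoring plan already specifies this split, cite it instead.

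The cost is a sentence and a few table rows. Treatment data are recorded in the mobile application (Protocol 6.12.7), and masking already assigns "upper- and lower-case letters to each trial, age group, and treatment arm" (Protocol 4.4.3.3). One condition needs checking: the documents do not say that event reports record age at dosing or link to the treatment record, and each report must do one or the other. The remaining downside is sparse cells, which the table should present as counts with denominators.

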### 3.5.6. Statistical software

Statistical analysis will be conducted using R (R Foundation for Statistical Computing, Vienna, Austria).

## 5. Revision history

Version	Date	Summary of Changes, Justification, and Timing vis-à-vis key trial events (enrollment completion, interim analyses, unmasking, etc)
1	2020-03-10	
 
First draft
 

2	2020-03-30	
 
Revision to sample size calculations (harmonization across work to date)
 
Revision to adaptive allocation algorithm text
 
Revision to analysis details (phase-stratified estimator)
 

3	2020-05-01	
 
Harmonized the order of outcomes, and list of secondary outcomes with protocol v1. Added a complete list of pre-specified secondary analyses.
 
Added language to allow for communities to contribute to the primary outcome if they were missed in a single census but revisited after ~12 months from the last census.
 

4	2020-07-27	
 
Added implementation trial to the SAP
 
Updated sample size and detectable effect calculations based on the revised design, which now includes a mortality trial and a parallel implementation trial.
 
Described the resistance monitoring as nested within the mortality trial.
 
Changed the hypothesis testing framework from Bonferroni-Holm to a fixed sequence, hierarchical testing framework to maximize study power.
 
Added birth history outcome measurement for the implementation trial.
 

5	2020-07-31	
 
Added Figure 1 (design overview)
 

6	2020-08-05	
 
Added interim analysis (3.5)
 

7	2020-09-24	
Updated the design to reflect DSMC feedback, align with the Protocol:
 
 
Increased number of communities selected for mortality trial to 3,350
 
Delayed start of remainder of communities until 1.5 years after the first enrollment (aligned with interim analysis)
 
Simplified the comparison of delivery trial approaches to a 2-arm trial and removed mortality as an outcome
 

8	2020-10-08	Updated outcomes and additional analyses with relevant clarifications for costing and cost-effectiveness.
9	2021-04-06	
 
Added MORDOR continuation substudies to the outcomes definitions in section 6.1
 
Updated the multiple testing procedure planned for AMR substudy in section 4.1
 
Clarified the ITT analysis will only include enrolled grappes
 

10	2022-02-04	
 
Added sensitivity analyses to Delivery Trial treatment coverage outcome in section 6.2
 

11	2022-05-24	
 
• Updated the format to include 3 different sections for the 3 different trials.
 
• Added in the Programmatic Trial section.
 

12	2022-05-27	
 
• Removed details of CSI clinic visit outcome measurement and analyses until those details can be confirmed vis-à-vis field measurement and logistics.
 

13	2022-10-21	
 
• Updated wording of person-time calculations for Mortality trial
 

14	2023-07-24	
 
• Included in the trial overview details of study team masking (membership, timing, rationale), section 2.
 
• Updated Figure 1 and included footnote
 
• Updated the language of tempering roots from 1/3 or 1/4 to 1/4 or 1/6 or 1/8, section 3.2.2.
 
• Removed redundant paragraph for masking in the section of interim Analysis, section 3.2.5
 
• Clarified the timing of the primary analysis, to be exactly 2 years after completion of enrollment, section 3.2.6
 
• Revised Mortality trial primary analysis to align notation with the final adaptive randomization schedule, including the model specification and permutation test, section 3.5.2
 
• Moved Delivery Trial and Programmatic Trial analysis plans to separate SAPs to make the SAP easier to navigate.
 

15	2023-10-17	
 
• Updated Figure 1 to reflect the final count of communities screened and enrolled in the programmatic trial.
 

16	2024-09-25	
 
• Updated AMR sample size and power calculations. The lab is going to be processing all 150 communities for the AMR outcomes, so we can include the full 150 communities in the primary AMR analyses, as opposed to the 60 that we listed originally.
 

